5.1.2.4 Atezolizumab Clinical Studies Summary

Atezolizumab is currently being tested in multiple Phase I, II, and III studies, both as monotherapy and in combination with several anti-cancer therapies (see the Atezolizumab Investigator's Brochure for study descriptions). The single-agent safety and efficacy data available to date are from the following studies: one Phase Ia (Study PCD4989g) and two Phase II studies (Studies GO28625 [FIR] and GO28753 [POPLAR]).

Clinical benefit from atezolizumab monotherapy was observed in a broad range of malignancies including non-small cell lung cancer (NSCLC), renal cell carcinoma (RCC), melanoma, urothelial bladder cancer (UBC), head and neck cancer, gastric cancer, breast cancer and sarcoma. Results suggest that PD-L1 expression in the tumor microenvironment is associated with an increased probability of clinical benefit with atezolizumab.

Across all these patients, fatigue was the most frequently reported adverse event. Given the mechanism of action of atezolizumab, events associated with inflammation and/or immune-mediated adverse events have been monitored closely during the clinical program. These include potential dermatologic, hepatic, endocrine, gastrointestinal and respiratory events.

In trials investigating atezolizumab both as a single agent and in combination with chemotherapy, the incidence of adverse events in the treatment arms with combined use was consistent with the known safety profiles of the individual study drugs. Currently, no maximum tolerated dose, no dose-limiting toxicities and no clear dose-related trends in the incidence of adverse events have been determined.

Refer to the Atezolizumab Investigator's Brochure for additional details on clinical studies.

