5.2 Study Rationale

Treatment of TNBC represents a significant challenge due to the lack of clinically validated targets that are available for the other breast cancer subtypes. Preliminary data has indicated that treatment with immune checkpoint inhibitors targeting PD-1 such as pembrolizumab and PD-L1 such as atezolizumab results in approximately an 18-19% response rate in women with TNBC who also test positive for PD-L1 expression. While these data are promising, the benefit appears to be restricted to a relatively small fraction of the total TNBC patient population. Combination strategies to increase the clinical benefit of PD-1 / PD-L1 inhibitors in TNBC are the focus of intense research efforts. Preclinical testing in the 4T1 mouse model of TNBC indicate that entinostat combined with immune checkpoint blockade results in complete inhibition of primary tumors and metastases. The mechanism for this combined anti-tumor effect was determined to be entinostat's ability to inhibit the growth and function of MDSCs, an immune suppressor cell shown to block the anti-tumor T cell immune response. These data provide the basis for clinical testing of entinostat combined with atezolizumab in TNBC patients.

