7. PATIENT ELIGIBILITY

7.1 Inclusion Criteria

Patients meeting all of the following criteria are considered eligible to participate in the study:

1. Females aged 18 years or older on the day written informed consent is given.
2. Has histologically or cytologically confirmed triple negative breast adenocarcinoma that is either metastatic (stage IV of the TNM classification) or locally recurrent and not amenable to local curative treatment. TNBC diagnosis should be based on local laboratory ER/PgR/HER-2 tests and will be defined as HER2 negativity (IHC 0-1 and/or ISH non-amplification) and ER and PgR negativity (<1%). Disease must also be amenable to core biopsy (image-guided if applicable) at enrollment and for certain cohorts as described in the protocol, at least once during study treatment.
3. Evidence of measurable (according to RECIST version 1.1) locally recurrent or metastatic disease based on imaging studies (e.g., CT, MRI) within 28 days before enrollment/randomization.
4. Has received at least 1, but no more than 2, prior lines of systemic therapy for locally recurrent and/or metastatic disease
5. If patient has a history of treated asymptomatic CNS metastases they are eligible, provided they meet all of the following criteria:
 - Patient has measurable disease outside CNS;
 - Patient does not have metastases to midbrain, pons, medulla or spinal cord;
 - Patient is not on corticosteroids as therapy for CNS disease (anticonvulsants at a stable dose are allowed);
 - Patient has not had whole-brain radiation within 6 weeks prior to study enrollment;
 - Patient has stable CNS disease as demonstrated by at least 4 weeks of stability between the last intervention scan and the study screening scan
6. ECOG performance status of 0 or 1.
7. Has the following laboratory parameters within 21 days of enrollment:

System	Laboratory Value
Hematological	
Absolute neutrophil count (ANC)	$\geq 1.5 \times 10^9/L$
Platelets	$\geq 100 \times 10^9/L$
Hemoglobin	$\geq 9 \text{ g/dL}$ or $\geq 5.6 \text{ mmol/L}$
Renal	
Creatinine OR Measured or calculated ¹ creatinine clearance (CrCl) (glomerular filtration rate [GFR] can also be used in place of creatinine or CrCl)	$\leq 1.5 \times$ the upper limit of normal (ULN) OR $\geq 60 \text{ mL/min}$ for patient with creatinine levels $> 1.5 \times$ institutional ULN

System	Laboratory Value
Hepatic	

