7.2 Exclusion Criteria

Patients meeting any of the following criteria are not eligible for study participation:

1. Diagnosis of immunodeficiency or receiving systemic steroid therapy or any other form of immunosuppressive therapy within 7 days prior to the first dose of study drug. The use of physiologic doses of corticosteroids may be approved after consultation with the Medical Monitor.
2. Active autoimmune disease including active diverticulitis, symptomatic peptic ulcer disease, colitis, or inflammatory bowel disease that has required systemic treatment in past 2 years (i.e., with disease modifying agents, corticosteroids, or immunosuppressive drugs). Replacement therapy (e.g., thyroxine, insulin, or physiologic corticosteroid replacement therapy for adrenal or pituitary insufficiency) is not considered a form of systemic treatment.
3. Previously treated with a PD-1/PD-L1-blocking antibody (i.e., atezolizumab, nivolumab, pembrolizumab) or a histone deacetylase inhibitor (i.e., vorinostat, belinostat, romidepsin, panobinostat)
4. History or current evidence of any condition, therapy, or laboratory abnormality that might confound the results of the study, interfere with the patient's participation for the full duration of the study, or is not in the best interest of the patient to participate, in the opinion of the treating Investigator, including, but not limited to:
 - History of immune deficiencies or autoimmune disease (see Appendix 3 for complete list)
 - Myocardial infarction or arterial thromboembolic events within 6 months prior to enrollment or severe or unstable angina, New York Heart Association (NYHA) Class III (see Appendix I) or IV disease, or a QTc interval > 470 msec.
 - Uncontrolled hypertension or diabetes mellitus.
 - Another known malignancy that is progressing or requires active treatment (excluding adequately treated basal cell carcinoma or cervical intraepithelial neoplasia [CIN]/cervical carcinoma *in situ* or melanoma *in situ*). Prior history of other cancer is allowed, as long as there is no active disease within the prior 5 years.
 - Active infection requiring systemic therapy.
 - Known active central nervous system (CNS) metastases and/or carcinomatous meningitis. (see inclusion criterion 5)
5. Any contraindication to oral agents or significant nausea and vomiting, malabsorption, or significant small bowel resection that, in the opinion of the investigator, would preclude adequate absorption.

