10.4.2 Tumor Tissue

Fresh tumor tissue core biopsy samples will be collected during the study as follows:

- During **screening** from **all** patients on a **mandatory** basis.
- On **C2D15 (+/-3 days)** on an **optional** basis from patients in **the Dose Determination Phase**. Patients will be encouraged to provide an optional biopsy in order to help understand dose-immune correlate effects.
- On **C2D15 (+/-3 days)** on a **mandatory** basis until 20 samples are obtained in the Phase 2 portion of the study and on an **optional** basis for subsequent patients in this Phase 2 Expansion.
- At the time of progressive disease on an optional basis for all patients
- At the end of study treatment prior to the start of another systemic therapy, on an **optional** basis for all patients

Note: Archival tissue should also be collected at time of screening when available.

If, based on an interim review of tumor tissue data from the initial patients in Phase 2, such data are considered informative, then tumor tissue samples will be collected on a mandatory basis from all subsequent patients in the study. Alternatively, if such data are not considered informative, these samples will not be collected from subsequent patients.

Tissue samples will be sent to a central laboratory facility for preparation and distribution to other central laboratories for analysis. In addition to protein lysine acetylation testing, pre and post treatment tissue samples will also be analyzed for the following:

- PD-L1 expression level
- MDSCs – CD33+, S100A9+
- Macrophage – CD163+ or CD68+
- Neutrophil – Neutrophil elastase+
- CD8/Ki-76
- Dendritic cells – DC-SIGN (CD209)
- MHC class I
- FoxP3, CD4, CD8, granzyme B positive cells
- Gene expression – nanostring
- Whole exome sequencing and RNAseq

Refer to the Study Laboratory Manual for instructions on sample collection and shipment.

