In addition, Hazard Ratio for treatment effect will be estimated using a multivariate Cox proportional hazards model to be constructed by selecting variables among all the potential variables listed in the subgroup analysis (see Section 10.10) using stepwise selection method with entry p-value 0.05 and exit p-value 0.1. The treatment factor will be kept out of the model throughout the covariate selection process and only added into the final model. HR for treatment effect and corresponding 95% confidence interval (CI) will be estimated from the final model.

Note that a covariate may be removed from the analysis if the number of patients/events representing one level of that variable is insufficient or data collected on that variable are insufficient.

A sensitivity analysis will be performed to assess the impact of the different censoring mechanisms and deviations from the planned schedule of disease assessments; refer to Table 2.

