10.10 Subgroup Analysis

Subgroup analyses will be done for PFS and OS to assess internal consistency of study results and whether there is significant treatment heterogeneity across any of the subgroups. Tests within each subgroup and tests for subgroup-by-treatment-interaction terms will use an unstratified test from an unstratified Cox proportional hazards model. Additionally, these subgroup analyses will also be performed using a stratified test/model.

The following subgroup analyses are planned:

Table 3 – Planned Subgroup Analyses

Subgroup	Reason
Geographical region (US vs. Rest of World)	IWRS stratification factor
Prior endocrine therapy	Baseline demographic or prognostic factor
Prior chemotherapy	Baseline demographic or prognostic factor
Prior adjuvant/neoadjuvant systemic anticancer therapy	Baseline demographic or prognostic factor
ECOG 0 vs. ECOG 1	Baseline demographic or prognostic factor
Disease stage at study entry: unresectable locally recurrent vs. metastatic	Baseline demographic or prognostic factor
Number of metastatic sites: ≥ 3 vs. < 3 (based on the location/organ; i.e. 3 liver lesions count)	Baseline demographic or prognostic factor

**Statistical Analysis Plan
SNDX-275-0602 (TRIO025)
DM-025-037**

as 1 metastatic site)	
Disease-free interval: none, < 24 months, vs. > 24months (based on the first surgery expected to be curative, to the first relapse/progression date)	Baseline demographic or prognostic factor

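### SAP Table 3, the only covariate pool for the adjusted PFS model, omits baseline PD-L1 and number of prior lines, and lists prior chemotherapy without levels

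*SAP*

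**What the plan says.** **Adjusted model.** SAP 10.8.1 plans a multivariate Cox model for PFS, built by "selecting variables among all the potential variables listed in the subgroup analysis (see Section 10.10". Selection is stepwise (entry 0.05, exit 0.1), with treatment added at the end. A covariate may be removed if one level is too sparse.

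**Table 3 (SAP 10.10).** There are eight rows: region, prior endocrine therapy, "Prior chemotherapy", prior adjuvant/neoadjuvant therapy, ECOG, disease stage, number of metastatic sites and disease-free interval. The prior chemotherapy row has no levels. PD-L1 and number of prior lines do not appear. The same table governs the PFS and OS subgroup analyses.

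**PD-L1.** Protocol 5.1.2.4 reports that "PD-L1 expression in the tumor microenvironment is associated with an increased probability of clinical benefit with atezolizumab". Protocol 5.2 gives the TNBC response rate for PD-L1-positive women and adds that "the benefit appears to be restricted to a relatively small fraction of the total TNBC patient population". Protocol 10.4.2 makes a fresh screening biopsy mandatory for all patients and lists "PD-L1 expression level" among the tissue analyses. Protocol 7.1 and 7.2 set no PD-L1 criterion, and region is the only stratification factor.

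**Prior treatment.** Inclusion criterion 4 reads: "Has received at least 1, but no more than 2, prior lines of systemic therapy for locally recurrent and/or metastatic disease". The disease must be ER, PgR and HER2 negative. Exclusion criterion 3 rules out anyone "Previously treated with a PD-1/PD-L1-blocking antibody" or with an HDAC inhibitor. SAP 10.4 summarises prior regimens descriptively.

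**The concern.** Both arms receive atezolizumab. A factor that the protocol itself links to atezolizumab benefit is therefore a natural candidate prognostic factor for PFS, and nothing in eligibility or randomization controls it. With 35 patients per arm it can fall unevenly by chance. The adjusted model is where this SAP would examine such an imbalance, and as written it cannot, because PD-L1 is not among its candidates. The same holds for 1 versus 2 prior lines, the treatment-history contrast that eligibility builds into the population.

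Meanwhile one Table 3 row may carry little information. If prior chemotherapy means yes/no, a population with triple-negative advanced disease and at least one prior systemic line should contain few patients in the no group.

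At stake is how the one realised trial is read, not the validity of the primary test. Factors added after unblinding would be post hoc.

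**Working it through.** **1. The design figure reproduces.** Protocol 13.1.2 and 13.2 give medians of 4 and 7 months, one-sided alpha 0.10, 80% power, 60 events and one O'Brien-Fleming look at 45. Fixed design: 4 × (1.2816 + 0.8416)² / (ln 4/7)² = 4 × 4.508 / 0.3132 = 57.6, so 58 events. With a Lan-DeMets O'Brien-Fleming look at 75% information, 59.7 events are needed and 60 give 80.1% power. Nothing below disputes this.

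**2. Assumptions.** The documents give neither PD-L1 prevalence nor a PFS hazard ratio for PD-L1. I assume prevalence of 30–60% (40% in the simulations) and a hazard ratio of 0.5–0.6 for positive versus negative. Minimization uses region only, so PD-L1 is treated as falling at random.

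**3. Chance of imbalance.** Let D be the difference in PD-L1-positive counts between two arms of 35. Its standard deviation is √(70 × p × (1 − p)), which is √(70 × 0.24) = 4.10 at p = 0.4. The normal approximation gives P(D ≥ 7) = 1 − Φ(6.5 / 4.10) = 0.056. Exact binomial results:

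| Prevalence | Gap ≥ 6, either way | Gap ≥ 7, either way | Gap ≥ 7, one named direction |
|---|---|---|---|
| 30% | 15.1% | 8.9% | 4.5% |
| 40% | 17.9% | 11.2% | 5.6% |
| 50% | 18.8% | 12.0% | 6.0% |
| 60% | 17.9% | 11.2% | 5.6% |

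**4. Averaged over randomizations.** Simulation used 35 per arm and exponential PFS, stopping either at 60 events or after 9 + 9 months. One-sided error with PD-L1 ignored is 9–11%. At hazard ratio 4/7, power is about 74–78% ignoring PD-L1 and 78–80% stratifying on it. The loss is about 1 point at a PD-L1 hazard ratio of 0.6 and about 3 at 0.5, or 4 at 0.5 when stopping at exactly 60 events.

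**5. Given a 7-patient gap.** The tests are at one-sided 10%, from log-rank and Cox runs. The ranges cover PD-L1 hazard ratios of 0.5–0.6 and the different set-ups.

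| PD-L1-positive, entinostat vs placebo | Treatment effect | Unadjusted | Adjusted for PD-L1 |
|---|---|---|---|
| 18 vs 11 | none | error about 17–23%; HR 0.87–0.90 | error about 10%; HR about 1.00 |
| 11 vs 18 | HR 4/7 | power about 55–67% | power about 76–80% |

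**6. Subgroup rows.** If a level holds 30–70% of patients, it holds about 60 × 0.3 = 18 to 60 × 0.7 = 42 events. Power within a level at HR 0.57 is about 46% with 18 events, 60% with 30 and 70% with 42. The standard error of the log interaction runs from √(4/30 + 4/30) = 0.52 to √(4/18 + 4/42) = 0.56. The ratio of hazard ratios detectable with 80% power is therefore about exp(−2.123 × 0.56) = 0.30 to exp(−2.123 × 0.52) = 0.33.

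**7. Prior chemotherapy as yes/no.** If 95–99% are yes (assumed), the no level holds 70 × 0.05 = 3.5 to 70 × 0.01 = 0.7 patients, and 3 to 0.6 of the 60 events.

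**8. Listing versus including.** Suppose 24 of 60 events are in PD-L1-positive patients. The standard error of the PD-L1 log hazard ratio is then about √(1/24 + 1/36) = 0.264. The chance of passing entry at 0.05 is roughly Φ(0.693/0.264 − 1.96) = 75% at a hazard ratio of 0.5 and Φ(0.511/0.264 − 1.96) = 49% at 0.6. Listing PD-L1 without specifying its inclusion would leave the adjustment partly to chance.

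**The case against.** **PD-L1 may be planned elsewhere.** Protocol 13.5.8 allows associations between immune correlates and clinical outcomes to be explored, the SAP sends exploratory and correlative work to separate documents, and the exploratory objectives are redacted. This stands. The omission is shown for Table 3 and this Cox model, and a reader should not infer that the programme ignores PD-L1.

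**The design is valid without PD-L1.** This also stands. A reader might infer from step 5 that the primary test is inflated. It is not: those figures are conditional on one unlucky draw, and similar figures could be produced for any unlisted prognostic factor. Nor should the 15–19% chance of a 6-patient gap in either direction be attached to harm that needs a 7-patient gap in one direction.

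**The protocol's PD-L1 statements are modest.** They report an association across tumour types and a response rate in PD-L1-positive TNBC, with no PD-L1-negative comparator and no PFS figure. They do not establish that benefit depends on PD-L1.

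**Near-constant prior chemotherapy is an inference.** Criterion 4 says systemic therapy, and the washout exclusions anticipate prior antibodies and targeted agents. If the row means setting or number of regimens, it varies. The SAP permits removal of a sparse covariate but does not require it. So the documents do not support saying that the row has no comparison group or will be dropped, only that its levels need defining.

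**Forcing covariates is an analyst's choice.** True. Step 8 is a reason to prefer it, not proof of an error. No harm has been quantified for prior lines; the case for that factor is that eligibility creates the contrast and the data are collected.

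**Conclusion.** The point holds for the supportive adjusted model and the PFS and OS subgroup analyses. Table 3 leaves out two baseline factors that are already collected, one of them tied by the protocol to the drug given in both arms, and it carries an undefined row that is probably near-constant if read as yes/no.

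The primary stratified log-rank test, its alpha and the 60 events are unaffected. On average, ignoring PD-L1 leaves error near 10% and costs a few points of power at most. The benefit of the change is confined to interpreting a trial with a chance imbalance. A 7-patient or larger gap in a given direction has probability about 4.5–6%. With an 18 versus 11 split, adjustment brings conditional error from about 17–23% back to about 10%; with the reverse split it recovers power from about 55–67% to about 76–80%. These sizes rest on the assumed prevalence and PD-L1 hazard ratio and would shrink with a weaker factor.

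This is an improvement worth making before unblinding, not a condition for the trial's validity.

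**What to change.** In SAP Table 3:
- Add baseline PD-L1 from the screening biopsy, positive versus negative, with assay and cut-off fixed before unblinding and a stated rule for missing results.
- Add number of prior lines for locally recurrent or metastatic disease, 1 versus 2.
- Define the levels of prior chemotherapy, or drop the row.

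In SAP 10.8.1, include both added factors in the supportive adjusted Cox model. Report their balance by arm; the planned prior-therapy table by treatment group already covers part of this. Label the subgroup results descriptive. If a separate correlative plan already specifies a PD-L1-adjusted PFS analysis, cross-reference it. Leave the primary test, alpha and 60 events unchanged.

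Cost: SAP wording and transfer of the baseline PD-L1 result into the analysis dataset before the 45- and 60-event cut-offs. Some biopsies will be unevaluable. No new procedure or patient is needed.

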13.1.2 Expansion Phase

The Expansion Phase will evaluate the efficacy and safety of entinostat when administered at the recommended Phase 2 dose with atezolizumab in a randomized, double-blind, placebo-controlled setting. Up to 70 eligible patients with metastatic TNBC will be randomized to receive atezolizumab with entinostat or placebo in a 1:1 allocation.

The true median PFS for patients with aTNBC receiving atezolizumab monotherapy is expected to be approximately 4 months from the initiation of such treatment. It is hypothesized that the combination of entinostat and atezolizumab will improve true median PFS by 3 months (i.e., from 4 to 7 months). Under the exponential distribution, such an improvement in median PFS represents a reduction of 43% for the true PFS failure hazard rate or equivalently, a hazard ratio of 0.57. Inferential comparisons will be performed using a stratified log-rank test, stratifying on the randomization stratification factor of geographic location. Total information of 60 PFS failures, defined as documented progressive disease by RECIST 1.1 or death due to any cause

without documented progressive disease beforehand, is estimated to provide 80% power to detect a 43% reduction in the PFS failure hazard rate with 1-sided significance level of 0.1 (SEQDESIGN procedure, SAS version 9.2).

Assuming approximately 9 months of accrual and an additional 9 months of follow-up, total accrual of 70 patients (approximately 35 per treatment arm) is projected to result in 60 PFS failures within approximately 18 months of the first patient randomization. Patients who discontinue study treatment for reasons not due to documented progressive disease by RECIST 1.1 will continue to undergo disease assessments until the earlier of documented progressive disease, death, or withdrawal of consent/lost to follow-up. It is anticipated that the number of patients who will drop out of the study without PFS failure beforehand will be low (2–3%). Depending on the actual number of such dropouts, the number of patients accrued may be increased by 6–10 additional patients to accommodate for a higher-than-expected number of dropouts.

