13.2 Phase 2 Interim Efficacy Analyses

The sample size and number of PFS failures were adjusted using the O'Brien -Fleming group sequential procedure to account for 1 planned interim analysis of PFS after 45 events (75% information). It is projected that 75% and 100% of total information will be reported at approximately 12 and 18 months, respectively.

The interim analysis will be performed to support the Sponsor's product development plans and ongoing resourcing activities. Although there are no plans to terminate the study early because of early evidence of superior efficacy for the combination treatment, the significance levels at the interim analysis and final analysis will be adjusted to maintain control of the overall type I error rate for multiple testing of PFS (O'Brien 1979).

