5.2.2 Phase 2 Expansion Phase

The following assumptions are made:

- Patients in the control arm have true median PFS of 4 months
- Patients in the experimental arm have true median PFS of 7 months (under exponential distribution, true PFS hazard ratio of 0.57)
- Expected accrual duration will be 9 months and an additional 9 months of follow-up. The α type I error rate is set to 10% (1-sided)
- The β type II error rate is set to 20% (i.e. the power of the trial will be 80%)

Under these assumptions, 70 patients (35 per arm) will be enrolled in the trial, which is projected to result in 60 PFS failures, defined as documented disease progression by RECIST 1.1 or death due to any cause without documented disease progression beforehand, within approximately 18 months of the first patient randomized.

It is anticipated that the number of patients that drop out without PFS failure will be low (2-3%). Depending on the actual number of such dropouts, the number of patients accrued maybe increased by 6-10 patients to accommodate for a higher-than-expected number of dropouts.

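### The supplementary adjusted Cox model selects covariates by stepwise p-values and need not include region, the only randomization factor, so its hazard ratio comes from a model not known in advance

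*SAP*

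**What the plan says.** The main inference for PFS is a log-rank test stratified by geographic location. The main hazard ratio comes from a Cox model stratified the same way with no further covariates (Protocol 13.5.5; SAP 10.8.1).

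SAP 10.8.1 then adds a multivariable Cox model that the protocol does not mention. Its covariates are drawn from the subgroup variables of SAP 10.10, Table 3, "using stepwise selection method with entry p-value 0.05 and exit p-value 0.1". On treatment it says "The treatment factor will be kept out of the model throughout the covariate selection process"; treatment is added to the selected model at the end, and a hazard ratio with a 95% interval is reported. A covariate may also be removed when numbers in a level are too small, with no threshold given.

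Table 3 has eight candidates. The first is "Geographical region (US vs. Rest of World"), which SAP 5.3 gives as the only factor balanced at randomization. The text on the adjusted model neither keeps region in nor stratifies by it, whereas the example code for the main Cox model has an explicit strata statement. SAP 10.8.4 applies the PFS methods to OS.

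**The concern.** A Cox hazard ratio for treatment changes its meaning with the covariates it conditions on. Here those covariates are decided by p-values from about 60 events, so nobody can say in advance what the adjusted hazard ratio will be adjusted for. Region may drop out. The main and adjusted estimates would then differ in two ways at once: the added covariates, and whether region is accounted for.

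Selection on association with outcome also does not target chance imbalance. A factor that is imbalanced and moderately prognostic can miss p<0.05 and be left out. In a trial where "70 patients (35 per arm) will be enrolled in the trial", balanced on one factor, this is the only planned covariate-adjusted estimate of the overall PFS effect, so its composition is worth settling beforehand. If the model is also run at the 45-event interim, which the SAP does not exclude, the covariate set could differ between the two looks.

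**Working it through.** **1. The plan's own figure.** Inputs from Protocol 13.1.2: "a hazard ratio of 0.57" (medians 4 and 7 months, 4/7 = 0.571), "Total information of 60 PFS failures", and "80% power to detect a 43% reduction in the PFS failure hazard rate with 1-sided significance level of 0.1". Schoenfeld's formula gives

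d = 4(z₀.₉₀ + z₀.₈₀)² / (ln HR)² = 4(1.2816 + 0.8416)² / (0.5596)² = 18.03 / 0.3132 = 57.6, so 58 events.

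With the O'Brien-Fleming look at 45 of 60 events (Protocol 13.2), 59.6 events are needed, and 60 events give 80.2% power. The plan's figure is reproduced. The sample size is not in question; 60 events is the information available for selection.

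**2. Chance that one real binary factor enters.** With prevalence p and two-sided entry at 0.05:

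P(enter) = Φ(√(60·p(1−p))·|ln HR| − 1.96).

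For p = 0.5 and HR 1.5: √15 × 0.4055 − 1.96 = −0.39, so 35%. The 50% break-even is HR = exp(1.96/√(60·p(1−p))); for p = 0.5 it is exp(1.96/3.873) = 1.66.

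| Split | HR 1.5 | HR 2.0 | HR 2.5 | HR for 50% entry |
|---|---|---|---|---|
| 50/50 | 35% | 77% | 94% | 1.66 |
| 20/80 | 24% | 57% | 81% | 1.88 |
| 10/90 | 15% | 36% | 57% | 2.32 |

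**3. Chance that noise enters.** With eight independent irrelevant candidates, 1 − 0.95⁸ = 34%.

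**4. Simulation of the SAP algorithm.** 70 patients, cut at the 60th event, minimization at 0.80 on region, eight candidates, score-test entry at 0.05, Wald exit at 0.10, treatment added last, 1,500 trials per scenario.

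Assumptions not in the documents:
- independent covariates, exponential times, no dropout;
- prevalences: region 50%, prior endocrine therapy 15%, prior chemotherapy 90%, prior adjuvant/neoadjuvant therapy 70%, ECOG 1 40%, locally recurrent 15%, three or more sites 50%, disease-free interval 30/40/30;
- factors with fewer than 5 patients in a level removed;
- region, ECOG status and number of sites truly prognostic, with a common HR.

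Ranges cover treatment HR 1.0 and 0.571.

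| Factor HR | Region kept | Each real factor kept | All three kept | ≥1 noise variable |
|---|---|---|---|---|
| 1.5 | 29–31% | 28–33% | 3–4% | 28–29% |
| 2.0 | 67–69% | 64–72% | 30–38% | 28–30% |
| 2.5 | 88–89% | 87–90% | 70–76% | 29–30% |

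With no real factor, region is kept in about 5% of trials and at least one variable enters in 35–37%. Between 57 and 101 different final models appear per 1,500 trials. Over all settings tried, including one with eight binary candidates, region is kept in about 27–32% at HR 1.5 and 62–69% at HR 2.0, and noise enters in about 27–37%.

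**5. Effect on the treatment estimate (true HR 0.571).** The fixed model here contains region, ECOG status and sites. Cells give median HR, then rejection rate at one-sided 0.10.

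| Factor HR | Stepwise | Main stratified Cox | Fixed |
|---|---|---|---|
| 1.5 | 0.595, 75% | 0.597, 76% | 0.567, 79% |
| 2.0 | 0.586, 78% | 0.612, 72% | 0.558, 81% |

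Simulation error is about 1 point on power. Under no treatment effect, stepwise rejects in 9.9–11.5% of trials and the fixed model in 10.1–11.8% (nominal 10%). Stepwise 95% intervals cover 94–95%.

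**6. Standard error, and dependence on the choice of factors.** With eight evenly split binary candidates, region HR 1.5 and two factors at HR 1.8, the mean standard error of the log hazard ratio is 0.272 for stepwise and 0.281 for a fixed model holding exactly the real factors. For a region-stratified model with ECOG status, sites and disease-free interval it is 0.289. Power of that last model against stepwise is 78.9% vs 75.9% if both real factors are on its list, 75.1% vs 74.4% if one is, and 73.6% vs 74.9% if neither is.

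**The case against.** The case for leaving the plan alone is substantial. The model is an addition to the main analysis, and the SAP plans an estimate and interval from it, not a test, so power is an indirect yardstick. The algorithm is pre-specified: candidates, thresholds and the exclusion of treatment from selection are all written down. Region is already handled by minimization and by stratifying the primary test and main hazard ratio. Stepwise also does about as well as, or better than, the main stratified Cox model (75% vs 76%; 78% vs 72%). All of this stands, and it keeps the point minor.

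A reader might infer more than the documents support:

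- **That selection usually omits the real prognostic factors.** This depends on effect sizes the documents do not give. An evenly split factor has a better than even chance of entry once its HR exceeds about 1.66. In the setting of step 6, each HR-1.8 factor was kept in 52% of trials, although both were kept together in only 29%.
- **That a fixed model gives a more precise estimate.** The standard errors in step 6 point slightly the other way. What adjustment for real factors does in a Cox model is reduce attenuation of the hazard ratio.
- **That this model is the only safeguard against chance imbalance.** Baseline characteristics are tabulated by arm (SAP 10.2), and treatment effects are examined within every Table 3 factor (SAP 10.10). These are not adjusted estimates of the overall effect, but they do look at imbalance and consistency.

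What the objection does not answer is that the adjusted model can leave out the factor the trial randomizes by, and that its content is unknown until the data are seen.

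**Conclusion.** The point holds as a minor one. The adjusted PFS and OS hazard ratios come from data-selected models that may not condition on region. Under the assumed effects, region is lost in roughly two thirds to three quarters of trials at HR 1.5 and roughly a third at HR 2.0. The full set of three real factors is rarely recovered unless effects are large, and an irrelevant variable enters in about 27–37% of trials.

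The consequence is an unstable and somewhat attenuated supplementary estimate (median 0.595 against 0.567 at factor HR 1.5). It is not a loss of error control: type I error and coverage are essentially nominal, and the primary stratified log-rank test and stratified Cox hazard ratio are untouched. The gain of about 2–4 points of power, and the reduced attenuation, arise only if the pre-chosen factors are prognostic. The percentages rest on assumed effect sizes, prevalences and independence; that region is only a candidate follows from the SAP text itself.

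**What to change.** In SAP 10.8.1, stratify the adjusted Cox model by geographic region and replace stepwise selection with a short covariate list fixed before unblinding, hence before the 45-event interim. ECOG (0 vs 1) and number of metastatic sites (≥3 vs <3) are examples already in Table 3. Label the model supportive, and apply the same wording to OS.

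The list should stay short. All Table 3 variables amount to nine coefficients, because disease-free interval has three levels; with treatment that is ten, or 60/10 = 6 events per coefficient. The two-factor example has three coefficients, or 60/3 = 20 events each. If disease-free interval is wanted, its categories first need to place exactly 24 months, which Table 3 leaves unassigned.

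The cost is about one sentence in the SAP and simpler programming, using variables already planned for analysis. The downside is that a pre-chosen factor may prove non-prognostic and slightly widen the interval. The documents do not establish which Table 3 factors are prognostic, so the choice should be made and justified by the study team.
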